7.6 Follow-up

Patients will be followed every month (± 1 week) for 3 months and then every 3 months thereafter from the date of last dose of nivolumab for up to 2 years. A research blood sample will be taken 1 year after the first dose of nivolumab. A phone call may be used to assess survival and to record initiation of an alternative form of treatment for lymphoma after response assessment at 1 year post-ASCT.

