9. RESPONSE EVALUATIONS AND MEASUREMENTS

Lymphoma progression will be assessed using the Recommendations for Initial Evaluation, Staging, and Response Assessment of Hodgkin and Non-Hodgkin Lymphoma: The Lugano Classification (Cheson et al. 2014, see Appendix F). Progression will be assessed 6 months post-ASCT and 1 year post-ASCT.

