10.2 Sample Size Considerations

The null hypothesis to be tested is that the true 12-month PFS is 50% against a two-sided alternative hypothesis of a 70% PFS rate. The 50% 6-month PFS rate was obtained from the Recommendations for Initial Evaluation, Staging, and Response Assessment of Hodgkin and Non-Hodgkin Lymphoma: The Lugano Classification (Cheson et al. 2014, see Appendix F). A two-sided, one-sample log-rank test calculated from a sample of 36 evaluable subjects achieves 80.3% power at a 0.050 significance level to detect an improvement of 20% in 12-month PFS.

The probability that a subject experiences an event during the study is 0.4579. The expected number of events during the study is 16. It is assumed that the survival time distributions of both groups are approximated reasonably well by the Weibull distribution with a shape parameter of 1.00. These proportions assume an enrollment period of 18 months and a follow-up period of 12 months after the last subject is added. In order to allow for a 10% dropout rate, a total of 40 patients will be enrolled. The sample size was calculated using PASS version 14.

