10.4.2 Efficacy Analysis

The primary efficacy analysis will be performed using the FAS. Sensitivity analyses will be performed using the Efficacy-Evaluable Population (EFF).

- Progression-Free Survival (PFS), defined as the time from the first day of study drug administration (Day 1) to disease progression as defined by the Recommendations for Initial Evaluation, Staging, and Response Assessment of Hodgkin and Non-Hodgkin Lymphoma: The Lugano Classification (Cheson et al. 2014, see Appendix F), or death on study. Patients who are alive and free from disease progression will be censored at the date of last tumor assessment.

For PFS Kaplan-Meier curves will be generated and the median time to event and the associated 95% CI be provided. Kaplan-Meier estimates will also be produced for the following specified time points: 12 months and 24 months. The hazard ratio and the 95% CI for these endpoints between the two treatment groups will be calculated.

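### Section 10.4.2 puts no limit on how long after the last scan a death still counts in PFS, so one late death can take the 24-month Kaplan-Meier estimate to zero

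*Combined protocol and SAP*

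**What the plan says.** Section 10.4.2 starts PFS at the first day of study drug and ends it at Lugano progression or death on study. For the rest: "Patients who are alive and free from disease progression will be censored at the date of last tumor assessment". It then plans two landmark figures: "Kaplan-Meier estimates will also be produced for the following specified time points: 12 months and 24 months".

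On scanning, Section 9 says "Progression will be assessed 6 months post-ASCT and 1 year post-ASCT". Section 7.5 also requires a scan after transplant and before treatment, and otherwise leaves PET-CT to institutional standard of care. It requires no scan after 1 year.

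Follow-up under Section 7.6 lasts up to 2 years from the last dose. After the 1-year response assessment, "A phone call may be used to assess survival" and any new lymphoma treatment.

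Section 10.4.2 does not define which deaths are on study and sets no maximum interval between the last scan and a counted death. Section 2.2 gives the secondary objective as PFS at 12 months post-transplant, which is a different time origin from Section 10.4.2.

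**The concern.** Kaplan-Meier needs censoring that does not depend on what happens to the patient later. Here it may. A patient known by phone to be alive at month 24 is censored back at the 1-year scan, whereas a patient who dies at month 18 stays at risk until month 18. Among patients with no later scan, those still at risk after the 1-year assessment are then exactly those who will die. The estimate falls in large steps that ignore the event-free majority.

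What is at stake is a wrong published number: a 24-month PFS of 0% when about two thirds of patients are alive without documented progression. PFS is the only efficacy endpoint in Section 2.4.2.

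**Working it through.** **The plan's own figure.** Section 10.2 states "A two-sided, one-sample log-rank test calculated from a sample of 36 evaluable subjects achieves 80.3% power at a 0.050 significance level". Take exponential survival, 12-month PFS of 50% against 70% (hazard ratio ln 0.7 / ln 0.5 = 0.515), uniform accrual over 18 months and 12 months of further follow-up. The one-sample log-rank test with variance equal to the expected events under the null then gives power 0.803 at n = 36. The event probability is 0.4579 and expected events are 36 × 0.4579 = 16.5. The stated figures reproduce. They do not test the censoring rule.

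**Where the scans end on the first-dose clock.** Treatment starts 45 to 180 days post-transplant (Section 5). The 1-year scan therefore falls between day 365 − 180 = 185 and day 365 − 45 = 320 after first dose, or 6.1 to 10.5 months. Both planned landmarks, 12 and 24 months, lie beyond every patient's last required scan.

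**Closed form.** Let S* be the estimate once all event-free patients have been censored, and m the number of later counted deaths among patients with no later scan. After the j-th of these deaths the estimate is S* × (m − j)/m. At j = m it is 0, whatever S* was.

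**Example with 35 treated patients.** Ten progress before the 1-year scan, 24 are event-free, and one dies without progression at month 15.
- Before the death: 25/35 = 0.714.
- Rule as written, if the death counts: one patient at risk, so 0.714 × (1 − 1/1) = 0.
- For comparison, the 24 censored at last contact at month 24: 0.714 × (1 − 1/25) = 0.686.

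**How often.** The simulations use 35 patients, starts uniform on Day 45-180, the plan's 70% rate, last dose 168 days after first dose, and follow-up to 730 days after that. The documents give neither mortality without documented progression nor the frequency of later scans, so both are assumptions. Entries are the share of trials in which the 24-month estimate is exactly 0.

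| Deaths counted; clock; later scans | 1%/yr | 2%/yr | 4%/yr |
|---|---|---|---|
| All follow-up; transplant; none | 19% | 26% | 29% |
| All follow-up; first dose; none | 23% | 36% | 44% |
| All follow-up; transplant; 30% of patients scanned once more at 18 months | 10% | 15% | 19% |

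If deaths count only to 100 days after the last dose, with no later scans, the share is about 1-5% across these rates on the transplant clock and about 1% on the first-dose clock.

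A separate simulation on the first-dose clock assumed that 5-20% of events are deaths without progression. With one further scan for every patient at 12-24 months, the estimate was 0 in 5-16% of trials.

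**The narrow reading.** With the last dose at day 168, counted deaths end at day 168 + 100 = 268, or 8.8 months after first dose. Without later scans nobody is observed for PFS beyond 10.5 months, so the 24-month estimate is the last-scan value carried forward.

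**The 12-month landmark on the first-dose clock.** With all deaths counted and no later scans it was 0 in about 3% of trials.

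**The case against.** The strongest objection concerns which deaths count. A reader might infer that the rule dates deaths whenever they occur. Section 10.4.2 does not say so: it limits them to deaths on study. Section 11.3.4 uses that term next to the adverse-event reporting period, which ends 100 days after the last dose, and treats deaths in post-study survival follow-up separately. On that reading the collapse nearly disappears. This stands, and it is why the claim here is conditional. It does not rescue the 24-month figure, which is then unsupported by observation, and Section 10.4.2 itself leaves the term undefined.

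A reader might also infer a fault of the censoring rule independent of the scan schedule. That is not supported either. The same rule works acceptably when scanning continues through the reported time points, and later standard-of-care scans soften the effect. They are unscheduled, however, so the plan cannot rely on them.

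A third objection is that the final analysis, triggered by the 12-month post-transplant assessment (Section 10.5.1), would cut off late deaths. Early enrollees still have long follow-up by then. With a cut at the last patient's 1-year scan and 24 months' accrual, the 24-month estimate was 0 in 16%, 30% and 42% of trials on the transplant clock when all deaths counted.

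Finally, safety is the primary objective, and the secondary objective is 12 months post-transplant, when a scan is required. This limits the severity.

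**Conclusion.** The concern holds conditionally. If on-study deaths include the 2-year follow-up, the 24-month estimate can collapse to 0 on a single late death: about 19-29% of trials on the transplant clock and 23-44% on the protocol's first-dose clock, at assumed mortality of 1-4% a year with no later scans, and less with them. If on-study deaths end 100 days after the last dose, collapse is rare (about 1-5%), but the figure adds nothing to the last-scan value. Under either reading no required scan supports a 24-month PFS.

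A reader might go further and call the 12-month first-dose estimate equally worthless. The roughly 3% collapse rate does not support that. The valid point is that it lies beyond every required scan.

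This should be fixed, but it does not threaten the primary objective.

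**What to change.** In Section 10.4.2:
- Close PFS for every patient at the 1-year post-transplant assessment plus a stated visit window, for events and non-events alike, so that later deaths do not enter the curve.
- Estimate 12-month PFS from transplant, matching Section 2.2, with patients entering the risk set at first dose. Because nobody enters before the start window opens, the estimate is conditional on being event-free until then, and the report should say so. Without this change, the cut-off would leave the 12-month first-dose estimate beyond all PFS follow-up.
- Delete the 24-month PFS estimate and report 24-month overall survival from the follow-up already collected, censoring survivors at last contact.

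Defining on-study deaths, or counting deaths only within a stated interval of the last scan, would also prevent the collapse, but it would leave a 24-month PFS with no scan behind it.

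The cost is wording and no new data. PFS would not be reported at 24 months. Section 10.2 would also need restating: its 16 events assume 12 to 30 months of PFS follow-up per patient, whereas a 12-month close gives at most about 36 × (1 − 0.70) = 10.8 under the alternative. The required scans already imply that shortfall, and the change makes it explicit.

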5. STUDY DESIGN

This is a Phase II single-arm open-label study of nivolumab as maintenance therapy after autologous stem cell transplantation in patients with HL at risk of relapse or progression.

Patients will receive nivolumab (240 mg IV) every 2 weeks (± 2 days as long as interval between doses is 12-16 days) starting 45-180 days post-transplant for up to a maximum of 6 months of treatment. To compare immune recovery, a control group of 5 patients will receive standard-of-care procedures and treatment both pre- and post-transplant. Response to treatment for patients receiving study drug will be assessed 6 months and 1 year post-transplant using the Recommendations for Initial Evaluation, Staging, and Response Assessment of Hodgkin and Non-Hodgkin Lymphoma: The Lugano Classification (Cheson et al. 2014, see Appendix F).

The planned enrollment for this study is 40 patients: 35 patients receiving study drug and 5 patients will receive standard-of-care procedures and treatment both pre- and post-transplant.

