5.4.2 Immune Recovery versus Control Group

Correlative studies will compare immune recovery for 5 patients undergoing autologous stem cell transplant for HL but not receiving nivolumab (control) with patients receiving nivolumab as maintenance therapy (treatment). All pre- and post-transplant procedures in the control group will be according to standard-of-care as determined by their treating physician. When complete blood count (CBC) and comprehensive metabolic profiling (CMP) panels are collected results will be entered into the electronic case report form (eCRF) as part of the study record. Blood samples in control patients are to be collected at:

- Between days 45-180 after autologous stem cell transplant
- Every 2-4 weeks (± 5 days) while receiving study treatment based on standard-of-care schedule
- At 6 months (± 7 days) from first sample, and
- At 1 year (± 7 days) from first sample.

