10.3 Analysis Population

The following analysis populations will be used:

- Full Analysis Set (FAS) is defined as all subjects who have received at least one dose of study medication.

CONFIDENTIAL

STUDY DRUG: NIVOLUMAB

SARAH CANNON DEVELOPMENT INNOVATIONS STUDY NUMBER:

FINAL PROTOCOL DATE: 07 FEB 2020

BMT 24

VERSION 7

- Efficacy-Evaluable Population (EFF) is defined as all subjects receiving at least two cycles of study medication.
- Safety Population (SAF) is defined as all patients who have received at least one dose of study treatment. This population will be used for the safety analysis.

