10.5 Analysis Time Points

10.5.1 Final Analysis

The final analysis of the study will occur when all enrolled subjects have received at least 2 cycles of nivolumab and have completed 12 month post-ASCT disease assessment.

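### The planned between-group PFS hazard ratio and the final-analysis trigger cannot be carried out as written, and the null label, the PFS time origin and the 80.3% power need reconciling

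*Combined protocol and SAP*

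**What the plan says.** Section 5 describes the design: "This is a Phase II single-arm open-label study of nivolumab as maintenance therapy after autologous stem cell transplantation". It then splits enrollment: "The planned enrollment for this study is 40 patients: 35 patients receiving study drug", with the other 5 on standard of care. Section 5.4.2 describes that group as "5 patients undergoing autologous stem cell transplant for HL but not receiving nivolumab (control", followed for immune recovery through blood samples and routine laboratory results. On response, Section 5 says: "Response to treatment for patients receiving study drug will be assessed 6 months and 1 year post-transplant".

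Section 10.4.2 starts PFS at the first dose, censors at the last tumor assessment, uses the Full Analysis Set (FAS) first and the Efficacy-Evaluable Population (EFF) for sensitivity, and asks for Kaplan-Meier estimates at 12 and 24 months. It adds: "The hazard ratio and the 95% CI for these endpoints between the two treatment groups will be calculated". Section 10.3 says: "Full Analysis Set (FAS) is defined as all subjects who have received at least one dose of study medication". The EFF needs two cycles.

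Section 10.2 (repeated in the synopsis) sets 50% against 70% for 12-month PFS, then calls the 50% a 6-month rate. It powers "A two-sided, one-sample log-rank test calculated from a sample of 36 evaluable subjects" at 80.3%, two-sided 0.05, with 18 months of enrollment, 12 months of follow-up and 10% dropout from 40. The synopsis gives 2 years of enrollment. Section 2.2 counts the 12 months from transplant.

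Section 10.5.1 says: "The final analysis of the study will occur when all enrolled subjects have received at least 2 cycles of nivolumab" and have had the 12-month post-transplant disease assessment.

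**The concern.** Two rules cannot be executed. The efficacy section asks for a two-group comparison in a study with one treated group, and the data-cut rule sets a condition that part of the enrolled population can never meet. The one formal efficacy hypothesis also has two labels for its null rate and two starting points for its 12-month estimate, and its power was computed for more evaluable patients than will be treated.

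If these stay open, the comparison, the time origin, the null and the data cut would be settled after open-label outcomes are visible. PFS is the secondary objective. The safety summaries do not use the hazard ratio or the null, but Section 10.5.1 times the final analysis of the whole study, so its wording formally governs the safety analysis too.

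**Working it through.** **1. Hazard ratio.** A control patient would need three things to contribute to it:
- A start date: PFS begins at first study drug (10.4.2). Controls have none.
- Membership of an analysis set: FAS needs one dose and EFF two cycles (10.3). Controls in either: 0.
- Progression data: response is assessed in patients receiving study drug (5), and Appendix E is titled for them. Controls have only blood samples and laboratory results (5.4.2).

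**2. Trigger.** 40 − 35 = 5 enrolled patients can never have two cycles; 5/40 = 12.5%. Reading the rule as all treated patients does not repair it. One patient who stops after one cycle (still in the FAS), or who dies before the assessment, blocks it. If each treated patient independently reaches two cycles with probability 0.95 (assumption), all 35 do so with probability 0.95^35 = 17% (2.5% at 0.90; 49% at 0.98).

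**3. Null label and origin.** If 50% were the 6-month rate, the exponential 12-month null would be 0.5 × 0.5 = 25%.

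The last required scan is 1 year post-transplant (7.5, 9). Treatment starts on Day 45 to 180, so measured from first dose:
- earliest start: 12 − 45/30.44 = 10.5 months
- latest start: 12 − 180/30.44 = 6.1 months

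With the synopsis's 10-day window, the earliest start gives 12 − 35/30.44 = 10.9 months. No patient therefore has a required scan at 12 months from Day 1.

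The log-rank test differs from the Kaplan-Meier estimate here. Under the stated Weibull shape of 1.00 the null hazard is constant, so expected events are E = λ0 × total time at risk. If time at risk starts at first dose under either origin (delayed entry when the origin is transplant), observed and expected events are the same.

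**4. Power.** Inputs from 10.2:
- λ0 = ln 2/12 = 0.0578 per month; λ1 = −ln 0.7/12 = 0.0297; ratio λ1/λ0 = 0.5146
- Event probability with accrual 18 and follow-up 12: v1 = 1 − (e^(−12λ1) − e^(−30λ1))/(18λ1) = 0.4579, as stated
- Expected null events per patient: v0 = v1/0.5146 = 0.8898
- Variance of observed minus expected per patient under the alternative: σ² = v1 − v1² + 2A − v0² − 2B + 2·v0·v1. Here A and B are the integrals of G(u)·e^(−λ1u)·λ0²·u and G(u)·e^(−λ1u)·λ0·λ1·u over 0 to 30 months, and G(u) is the probability of follow-up beyond u. A = 0.5000 and B = 0.2573, so σ² = 0.7567 and σ = 0.8699.

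Power = Φ{[√n(v0 − v1) − 1.96√v0]/σ}

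| n | basis | z | power |
|---|---|---|---|
| 36 | stated in 10.2 | 0.7428/0.8699 = 0.854 | 80.3% (reproduces the plan) |
| 35 | all planned treated patients, no dropout | 0.7066/0.8699 = 0.812 | 79.2% |
| 32 | 35 × 0.9 = 31.5, rounded up | 0.5946/0.8699 = 0.684 | 75.3% |
| 31 | 31.5, rounded down | 0.5561/0.8699 = 0.639 | 73.9% |

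The plan's 36 is 40 × 0.9, which counts the 5 controls as if they could become evaluable. With 24-month accrual and the same 12-month follow-up, the formula (v1 = 0.4995, v0 = 0.9708, σ = 0.9366) gives 82.0% for 35, 78.4% for 32 and 77.0% for 31. The enrollment period therefore has to be settled before the figure is restated.

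**Sensitivity cases, by simulation** (n = 35, no dropout, uniform accrual, start day uniform over 45 to 180). With the full 12 months and 18-month accrual, the simulation gives 81%, about 2 points above the formula.
- Cut-off 12 months after the last transplant, all events captured: about 76% (14.0 events) with 18-month accrual; 79% to 80% (15.5 events) with 24-month accrual.
- No event, including death, captured after each patient's 1-year scan: about 47% (7.6 events).

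**The case against.** The two-group sentence and the trigger look like leftover or loose wording whose intent can be guessed. No power, error-rate or decision rule uses the hazard ratio, and Section 10.2 already gives the test, its level and its sidedness, so its absence from Section 10.4.2 is largely a matter of placement. All of that stands. It makes the correction easy, but the rules still need correcting. Section 10.4.4 defers only exploratory analyses to a later plan, so nothing supplied shows that the PFS rules will be put right elsewhere.

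It may be said that the controls could supply the second group. They could not as planned. Even with a start date and scans, and with controls on the null curve and treated patients on the alternative, there would be about 16.0 + 3.4 = 19.5 events (rounded). A true ratio of 0.515 would then have a 95% interval of roughly 0.16 to 1.65.

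A reader might infer that the scan schedule puts true power between 47% and 76%. The documents do not support that. The synopsis's 2-year enrollment lifts the upper case to 79% to 80%. The 47% case discards deaths, which Section 10.4.2 counts as events, and ignores the standard-of-care scans in Section 7.5. A reader might also infer that the conflicting origins undermine the log-rank test; under the stated constant hazard with delayed entry they do not.

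**Conclusion.** The point holds and should be fixed. The hazard ratio cannot be computed (0 controls in FAS or EFF), and the trigger cannot be met (at least 5 of 40 enrolled patients fail it permanently). Both follow directly from the text, with high confidence.

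The null label and the PFS origin are internal contradictions. The origin affects the 12-month Kaplan-Meier estimate, which from first dose lies beyond every patient's last required scan. Which label is right cannot be decided here, because the cited source is not available.

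The loss of power is modest: from 80.3% to 79.2% with 35 evaluable, and to about 74% to 75% with 10% dropout, under the plan's exponential curves, 18-month accrual and 12-month follow-up. The scan-schedule figures are sensitivity cases, not bounds on actual power.

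It would go too far to say that the study cannot be analyzed or that its safety objective fails. The trigger was probably meant for treated patients, and the safety summaries do not depend on the PFS comparison.

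**What to change.** - **10.4.2:** delete the hazard-ratio sentence and make the two-sided one-sample log-rank test of Section 10.2 the comparison, in the FAS with EFF as sensitivity.
- **10.5.1:** replace the trigger with: *when every patient who received nivolumab has completed the 12-month post-ASCT disease assessment or has progressed, died or left the study.*
- **10.2 and synopsis:** check the 50% against its source and give it one label. If it proves to be a 6-month rate, the null and the power must be recomputed.
- **2.2 and 10.4.2:** use one time origin. If transplant, start time at risk at first dose. If first dose, state that the 12-month estimate rests on assessments after the last required scan.
- **Power paragraph:** restate expected events and power for 35 treated patients with the intended dropout, and reconcile 18 months with 2 years of enrollment. Scan-schedule scenarios may be added if labeled as sensitivity cases.

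The cost is wording plus one recalculated paragraph, provided the 50% is confirmed as a 12-month rate. Adding tumor assessments after the 1-year scan would cost more, because Section 14.1 lists added tests or procedures as an amendment item. The corrections above do not require it.
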